Among humans, positive correlations were reported between bacterial diversity, butyrate-producing bacteria and cardiorespiratory fitness (VO₂max), and higher turnover of carbohydrates and proteins, and concentrations of short-chain fatty acids in athletes compared to sedentary controls. There is also growing evidence that physical activity status and exercise training may shape the gut microbiome (**Cataldi et al.,2022**).

Physical activity stimulates bacterial community richness by altering SCFAs-producing species, as well as favoring the colonization of health and athletic performance-promoting strains. The ability to promote a bacterial

composition capable of protecting the intestinal mucosa also it was found that the effects on gut microbiome seem to gradually disappear when the physical activity is no longer practiced (**Cataldi et al., 2022**).

Moderate aerobic exercise affects the intestinal system mainly through gut immune function gut barrier integrity through tight junction proteins expression and IgA production hypothalamic–pituitary–adrenal (HPA) axis stimulation which, in turn, affects enteric nervous system and intestinal transit time, as well as gut motility, intestinal pH and gut hormones release and bile acids metabolism within enterohepatic circulation (**Cella et al.,2021**).

High intensity interval training (HIIT) encompasses exercise prescriptions that are tailored to individual needs and can be used in most any exercise setting. This ability to adapt makes HIIT a valuable tool in the exercise programming of patients with a chronic disease. HIIT has a positive effect on the Bacteroidetes/Firmicutes ratio and also increased the alpha diversity in gut microbiota (**Denou et al.,2016**).

Chapter III

[figure not shown]
PATIENTS, MATERIALS AND METHODS

The current study is designed to compare between the effect of moderate continuous and high interval intensity training on gut dysbiosis and glucagon like peptide hormone in irritable bowel syndrome.

I. Patients:

This study will be carried out on sixty six irritable bowel syndrome patients of both sexes with an age range between twenty to forty five years. Patients will be recruited and practical work of the study will be carried out in national nutrition institute physiotherapy out clinic. Patient will be randomly assigned to three groups.

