To avoid type II error, sample size calculation is performed using G*POWER statistical software (version 3.1.9.2; Franz Faul, Universitat Kiel, Germany). To detect a large effect size of 0.4 with power of 80% and $\alpha=0.05$, the required sample size required for this study was $N=66$.

Ethical consideration:

- Approval of faculty ethical committee.
- The study procedure will be explained for all participants.
- Confidentiality will be assured.
- An informed consent will be taken from each subject prior to participation.

(Appendix I)

Criteria for the patient selection:

Inclusion criteria:

- 1) Patients will be selected with age range of 20 to 45 years of both genders.
- 2) Body mass index (BMI) will range from 30 to 34.9 kg\m².
- 3) Having more than one symptom for ROME IV for IBS diagnostic criteria **(Appendix II).**
- 4) Prediabetic with glycated hemoglobin HbA1c of 5.7 – 6.4.
- 5) Sedentary subjects with daily steps count less than five thousand steps measured by pedometer **(Prince et al.,2020).**

Exclusion criteria:

Patients with the following criteria will be excluded from the study:

- 1) Communication disorders
- 2) Gasterointestinal bleeding
- 3) Antibiotics or probiotics in the last 2 months
- 4) Recent surgeries in the last 6 months
- 5) Colorectal cancer or any terminal diseases
- 6) Fibromylgia or Multiple sclerosis
- 7) Palpable abdominal mass
- 8) Cardiovascular diseases

- 9) Active smokers
- 10) Musculoskeletal injuries that interfere with exercise program
- 11) Upper respiratory infections
- 12) Uncontrolled hypertension

Patients will be divided into 3 groups:

- **Group (A):** This group will include 22 patients with IBS. These patients will receive 40 minutes of MICT on the treadmill: 5 minutes of warm-up followed by 30 minutes of 65-75% of target heart rate ending with a 5 min cool-down period for 12 weeks along with following low FODMAP diet plan.
- **Group (B):** This group will include 22 patients with IBS. These patients will receive HIIT sessions consisting of a 30 minutes treadmill session a 5 minutes warm-up followed by 10 bouts of 1 minute at 90% of target heart rate interspersed by 10 bouts of 1 min of active recovery at 50% of target heart rate (totaling 20 min), and a 5 minutes cool-down period for 12 weeks along with following low FODMAP diet plan.
- **Group (C)** This group will include 22 patients with IBS. These patients will follow low FODMAP diet plan for 12 weeks

Materials and Methods

- **Evaluation**

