Out comes to be measured:

1) Primary outcomes

- a- Short chain fatty acids via gas chromatography
- b- Glucagon like peptide 1 via Elisa kit

2) Secondary outcomes

- a- Irritable bowel syndrome scoring system

- b- Irritable bowel syndrome quality of life questionnaire (IBS QoL)
- c- Change in body weight via body mass index (BMI)

Evaluation equipment and tools:

a) Gas chromatography: SCFAs butyrate and acetate

For SCFA analyses, fecal sample will be separated. Applying four analytes, including total SCFAs, acetate, propionate, and butyrate, will be targeted. Final concentrations will be calculated based on internal standards and are expressed as micromoles per gram of wet feces ($\mu\text{mol/g}$). Techniques and predictive approaches will be used across. gas chromatography will be used to quantify Short Chain Fatty Acids (SCFAs) from fecal samples (**Chen et al.,2021**).

b) Elisa Kit for serum GLP 1 hormone

This kit is an Enzyme-Linked Immunosorbent Assay (ELISA). The plate will be pre-coated with Human GLP-1 antibody (**Kuhre et al.,2015**).

c) Weight and Height measurements

Weight and height will be recorded to calculate body mass index (BMI) according to the following equation: (**Shukohifar et al.,2022**)

$$\text{BMI} = \text{weight}/\text{height}^2 \text{ (Kg/m}^2\text{)}.$$

d) IBS severity scoring system (Appendix III)

This five-item questionnaire will measure IBS symptom severity by addressing abdominal pain (frequency and severity), bloating, dissatisfaction with bowel habits, and interference with daily activities. Each question score ranges from 0 to 100 and a higher score indicates more severe GI symptoms. A total score of 75–175 represents mild IBS, 176–300 moderate IBS and >300 severe IBS (**Zeid et al.,2020**).

e) Irritable bowel syndrome quality of life questionnaire (IBS QoL) (Appendix IV)

The IBS-QoL is a condition-specific instrument will be used to assess the impact of IBS and effects of treatment. It consists of 34 questions which cover eight domains including dysphoria, interference with activity, body image, health worry, food avoidance, social reaction, sexual, and relationships. Each item has a five-point response scale (not at all, slightly, moderately, quite a bit, extremely). The responses are summed and averaged for a total score and transformed to a scale between 0 and 100: higher scores indicating better IBS-specific QoL (Hou et al.,2015).

3-Management procedure:

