After collecting the consent forms, will be examined by the researcher for the inclusion and exclusion criteria. Each eligible patient (according to the consent form and examination) will participate in the study.

Group A

Patients will receive moderate intensity continuous training (MICT).

The program will be in form of: (Clark et al.,2020).

- **Frequency:** Moderate continues training will be scheduled 3 times per week for 12 weeks
- **Intensity:** 65-75% of target heart rate.
- **Duration:** 40 minutes per session. Patients will be instructed to follow low fermentable short chain carbohydrates diet (low FODMAP) intervention for 12 weeks limiting daily fermented carbohydrate and dairy products intake and increase intake of protein, whole grains, fruits and vegetables

(Appendix V)

- **Group B**

Patients will receive high intensity interval training (HIIT)

The program will be in form of: **(Clark et al.,2020).**

- **Frequency:** High intensity interval training will be scheduled 3 times per week for 12 weeks
- **Intensity:** 90% of target heart rate including 10 bouts of 1 minute interspersed with 10 bouts of 1 minute of active recovery 50% of target heart rate.
- **Duration:** the session will last 30 minutes includes warming up and cooling down periods

Patients will be instructed to follow low fermentable short chain carbohydrates diet (low FODMAP) intervention for 12 weeks limiting daily fermented carbohydrate and dairy products and increase intake of protein, whole grains, fruits and vegetables

Group C

Patients will be instructed to follow low fermentable short chain carbohydrates diet (low FODMAP) intervention for 12 weeks limiting daily fermented carbohydrate and dairy products and increase intake of protein, whole grains, fruits and vegetables **(Vareny et al.,2017).**

Only the patients who will attend > 80% of the exercise training sessions will be included in this study.

Data Analysis and statistical design

- The collected data was analyzed using the statistical program SPSS ver. 20.0.
- The mean and standard deviation were calculated for all measured variables.
- Pearson correlation coefficient was used to determine the relationship between the measured variables.
- Statistical significance was set at $p < 0.05$.

REFERENCES

Aziz I & Simrén M (2021). The overlap between irritable bowel syndrome and organic gastrointestinal diseases. *The Lancet Gastroenterology & Hepatology*, 6(2), 139–148.

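### The analysis section specifies no between-arm model and no use of pre-treatment values; a baseline-adjusted comparison would usually be more precise at 22 per arm, provided baseline measurements exist

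*Combined protocol and SAP*

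**What the plan says.** The section on data analysis and statistical design has four lines: the SPSS version, the statement that "The mean and standard deviation were calculated for all measured variables", a Pearson correlation between measured variables, and a significance level of 0.05. No line compares the three arms, names a covariate or refers to a pre-treatment measurement.

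Elsewhere, three places bear on the point:

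- **Outcomes.** The primary outcomes are short-chain fatty acids (SCFA) and GLP-1. The secondary outcomes are IBS severity, IBS-QoL and "Change in body weight via body mass index (BMI"). Only the last is worded as a change. No assessment times are given for any outcome.
- **Eligibility.** "Body mass index (BMI) will range from 30 to 34.9" is an inclusion criterion, so BMI is certainly measured at entry. Nothing equivalent is stated for stool, serum or the questionnaires.
- **Design and sample size.** "Patient will be randomly assigned to three groups", with 22 patients in each and no stratification mentioned. The sample size is set "To detect a large effect size of 0.4 with power of 80" per cent and a 0.05 level, giving 66 patients. The test is not named.

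**The concern.** The question the trial asks is MICT against HIIT, which rests on 22 patients per arm. In a 12-week training and diet study, a patient's starting value usually predicts part of the end value. A model that includes it removes that part of the residual variance, and it removes the part of an observed difference that comes only from unequal starting levels.

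This would not be settled by naming a between-arm test. The test that matches the plan's own sample size is an unadjusted ANOVA, and the one outcome with a time element is a raw change. A sponsor who simply adds a test on end values or on changes would leave available precision unused. With no model written down, the choice among end values, changes and adjusted values could also be made after the data are seen.

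**Working it through.** **1. The plan's own figure.** Inputs from the sample-size paragraph: effect size 0.4 (read as Cohen's f, because the test is not named), power 80%, alpha 0.05. For a one-way ANOVA with three groups, the noncentrality is N × f². The smallest N reaching 80% is 64, and rounding up to equal groups gives 66. At N = 66 the noncentrality is 66 × 0.16 = 10.56 and power is 81.8%. So 66 is reproduced by an unadjusted three-group comparison with no baseline term.

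**2. Set-up for MICT versus HIIT.** n = 22 per arm, two-sided 0.05 (sidedness assumed), differences in SD units. The correlation r between pre-treatment and 12-week values is not in the documents, so a range is used. Variance of the estimated difference, relative to end values:

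- End values: 1, with 42 df.
- Change scores: 2(1 − r), with 42 df.
- Baseline-adjusted: (1 − r²)(1 + 1/40), with 41 df. The factor 1 + 1/40 is the small-sample price of chance baseline imbalance.

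Power comes from the noncentral t with noncentrality d × √(22/2) ÷ √(variance factor). At d = 0.8 on end values this is 0.8 × √11 = 2.65. Adjusted at r = 0.5, the factor is 0.75 × 1.025 = 0.769 and the noncentrality is 2.65 ÷ 0.877 = 3.03.

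**3. Power at a true difference of 0.8 SD.**

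| r (assumed) | End values | Change scores | Baseline-adjusted |
|---|---|---|---|
| 0 | 73.6% | 45.0% | 72.5% |
| 0.3 | 73.6% | 59.1% | 76.5% |
| 0.5 | 73.6% | 73.6% | 84.0% |
| 0.7 | 73.6% | 91.7% | 94.8% |

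The difference detectable with 80% power is 0.865 SD on end values. Adjusted, it is 0.876 SD at r = 0, 0.84 at r = 0.3 and 0.76 at r = 0.5.

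**4. Where adjustment stops paying.** Adjusted and end-value power are equal at about r = 0.16. Below that, the loss is at most 73.6 − 72.5 = 1.1 points. The critical t moves only from 2.018 to 2.020. Fitting all three arms together is slightly kinder: 74.3% unadjusted, 77.5% (r = 0.3) and 84.9% (r = 0.5) adjusted, with break-even at about r = 0.13.

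**5. Chance imbalance.** The standard error of a baseline difference is √(2/22) = 0.30 SD, so two arms differ by more than 0.4 SD in about 18% of randomisations. In simulation under a true null, an end-value test rejects in 7.5%, 11.3% and 17.2% of those imbalanced trials at r = 0.3, 0.5 and 0.7. In the other trials it rejects less than 5% of the time (3.6% at r = 0.5, 2.3% at r = 0.7), and over all randomisations the rate is about 5%.

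**The case against.** The strongest reply is that the plan contains no MICT-HIIT estimate, so nothing exists to lose precision. The basic defects are the missing comparison and the missing assessment schedule, and baseline adjustment is one line of their repair. That is fair as to cause. It does not remove the point, because the repair most consistent with the plan's sample size is an unadjusted one.

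Four stronger readings are tempting, and the documents do not support them:

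- **That the trial ignores pre-treatment values.** The BMI outcome is a change and needs a starting value. For the rest, four lines of silence show only that no use is specified.
- **That adjustment is always at least as precise.** At this size it is not: it loses slightly below about r = 0.16, and the gain at r = 0.3 is only about 3 power points. Nothing in the documents supports a high r for faecal SCFA or GLP-1.
- **That an unadjusted comparison inflates false positives.** The raised rates apply only to trials that happen to be imbalanced. Randomisation keeps an end-value test unbiased, at about 5% overall.
- **That the fix is free.** That is known only for BMI. If no pre-treatment stool or serum is planned, adjusting SCFA and GLP-1 would mean adding a sample of each per patient.

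**Conclusion.** The point holds as a gap in specification with a cost in precision. The plan states no between-arm model and no role for pre-treatment values, and its sample size assumes none. At 22 per arm and 0.8 SD, adjustment raises power from 73.6% to 76.5% at r = 0.3 or 84.0% at r = 0.5. Change scores would lower it to 59% at r = 0.3 and only match end values at r = 0.5, so extending the raw-change definition of the BMI outcome to the others is not an equal substitute.

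This rests on an assumed r, a two-sided test, full arms of 22 and pre-treatment measurements that the documents confirm only for BMI. The powers are upper limits if patients are lost, and no dropout allowance is stated. Adjustment protects against chance imbalance in the measured baseline value. It does not repair the selection created by keeping only patients who attend more than 80% of exercise sessions. The trial is not invalidated, but the change should be made before data are analysed.

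**What to change.** First, state for each outcome whether it is measured before treatment and at 12 weeks. Then add to the analysis section:

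> For each outcome with a pre-treatment measurement, the three arms are compared with a linear model of the 12-week value on arm and the pre-treatment value of the same variable. The adjusted MICT-HIIT difference is reported first, with its 95% confidence interval. Change scores are descriptive only, and baseline differences between arms are not tested.

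This covers BMI in any case, and SCFA, GLP-1, IBS severity and IBS-QoL if they are measured before treatment. The statistical cost is one degree of freedom per outcome, at worst about one power point. The model runs in the SPSS version already named and needs no further patients. Where no pre-treatment stool, serum or questionnaire is planned, the sponsor must either add that measurement or compare end values for that outcome and say so in advance.

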Moderate aerobic exercise affects the intestinal system mainly through gut immune function, gut barrier integrity, as well as gut motility, intestinal pH and gut hormones release; and bile acids metabolism within enterohepatic circulation (**Resende et al., 2021**).

Also High-intensity interval training is a popular, time-efficient mode of exercise to improve metabolic health and aerobic fitness, both of which have been associated with healthier gut bacterial community structure (**Rettedal et al., 2020**).

Statement of the Problem:

Is there a significant difference between the effect of moderate continuous versus high interval intensity training on gut dysbiosis and glucagon like peptide hormone in irritable bowel syndrome?

The Purpose of the Study:

To compare the effect of moderate continuous versus high interval intensity training on gut dysbiosis and glucagon like peptide hormone in irritable bowel syndrome.

Significance of the Study:

Irritable bowel syndrome affects around 11% of the global population with variation by geographic region: the highest in South America (21.0%) and the lowest occurring in South Asia (7.0%). In Egypt, the prevalence was 34% in primary healthcare center attendees. IBS significantly reduces work productivity and health-related quality of life (**Mohamed et al.,2021**).

The quality of life for patients suffering from IBS is greatly affected physically, psychologically, and economically. Several cases reported difficulties in concentration, decreased energy level, and lower self-esteem. In-addition IBS is

inducing occupational hazards as it affects the performance of patients at their jobs (**Elsayed et al.,2021**).

Although half of the cases referred to gastroenterologists is due to IBS, no clear etiology was found; however, some researches revealed that certain factors such as psychological factors, dietary habits, and exercise level were related to IBS onset and course (**Elhosseiny et al.,2019**).

Previous studies have been done separately on the effect of moderate intensity continuous training program and high intensity interval training on irritable bowel syndrome and gut dysbiosis, it is rational to compare between two training programs to know which is more effective to improve gut microbiota balance.

Delimitations:

This study will be delimited to the following aspects:

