Subjects will be delimited to patients with irritable bowel syndrome selected from the outpatient of national nutrition institute with the following criteria:

- Sixty six patients with irritable bowel syndrome of both genders.
- Their ages ranged from 20 to 45 years.
- Their Body mass index ranged from 30 to 34.9.
- Patients will be divided into 3 groups
 - **Group A:** Patients will receive moderate intensity continues training exercise program along with following Low fermentable, oligosaccharides, disaccharides, monosaccharides and polysaccharides diet plan (FODMAPs diet).
 - **Group B:** Patient will receive high intensity interval training exercise program along with following FODMAP diet plan.

- **Group C:** Patients will follow FODMAP diet plan only.
- Patients will be excluded if:
 - - Uncontrolled hypertension
 - - Gastrointestinal bleeding
 - - Colorectal cancer or any terminal diseases
 - - Communication disorders

Basic Assumptions:

It will be assumed that:

- 1) The primary medical assessment will be done to every participating patient who includes:
- 2) Complete medical history (personal, present and past)
- 3) All patients will stick to the program and will follow instructions.
- 4) All other factors which may influence the outcome such as noise and distraction will be controlled.

Hypothesis:

It will be hypothesized that there will be no significant difference between the moderate continuous versus high interval intensity training on gut dysbiosis and glucagon like peptide hormone in irritable bowel syndrome.

CHAPTER II

REVIEW OF LITERATURE

The human gastrointestinal (GI) tract represents one of the largest organ between the host, environmental factors and antigens in the human body. In an average life time, around 60 tonnes of food pass through the human GI tract, along with an abundance of microorganisms from the environment which impose a huge threat on gut integrity. The collection of bacteria, archaea and eukarya colonising the GI tract is termed the ‘gut microbiota’ and has co-evolved with the host over thousands of years to form an intricate and mutually beneficial relationship (**Thursby and Juge,2017**).

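### The analysis plan names no between-group estimate, interval or test; its only inferential method, Pearson correlation, cannot give the A versus B difference the trial is run to compare

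*Combined protocol and SAP*

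**What the plan says.** The Purpose of the Study is "To compare the effect of moderate continuous versus high interval intensity training on gut dysbiosis" and on glucagon-like peptide. The Hypothesis section puts the same comparison as a null: "there will be no significant difference between the moderate continuous versus high interval intensity training on gut dysbiosis and glucagon like peptide hormone". Under I. Patients, "Patient will be randomly assigned to three groups": A (moderate continuous training plus low-FODMAP diet), B (high-intensity interval training plus the diet) and C (diet only), with 22 patients each. The two primary outcomes, short chain fatty acids (SCFA) and GLP-1, are continuous.

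The section Data Analysis and statistical design has four bullets:

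- the software, SPSS version 20;
- "The mean and standard deviation were calculated for all measured variables", with no statement that this is done by group;
- "Pearson correlation coefficient was used to determine the relationship between the measured variables";
- a significance threshold of p<0.05, attached to no particular test.

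Two other places bear on the analysis. The sample-size paragraph reads "To detect a large effect size of 0.4 with power of 80" per cent and alpha 0.05, giving N=66, and names no test. The Management procedure ends with an attendance rule: "Only the patients who will attend > 80% of the exercise training sessions will be included in this study".

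**The concern.** The question concerns a difference between randomised groups, and the stated method concerns association between outcomes. Someone following the plan to the letter would report pooled or unspecified means and SDs and a set of correlations (for example SCFA with GLP-1), and would never compute A minus B.

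A comparison is clearly intended, so one will be made. The test, the contrast, the form of the outcome (end value or baseline-adjusted) and the patients included would then be settled with the data in hand. That is the risk prespecification exists to remove. The null wording of the hypothesis adds a second risk: without a planned confidence interval, a non-significant result can be misread as showing that the two programmes are equivalent.

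**Working it through.** **1. What is specified.** Searching the whole document for a t-test, ANOVA, ANCOVA, mixed model, contrast, between-group difference or confidence interval finds none. The analysis section runs complete from its heading to the reference list, so the gap is not due to missing text. Between-group analyses specified: 0.

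**2. Does the sample size supply the missing test?** Inputs from the sample-size paragraph and group descriptions: effect size 0.4, power 80%, alpha 0.05, N=66, three equal groups. The effect-size metric and the test family are not stated, so candidates were tried.

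- *Three-group one-way F test, Cohen's f=0.4.* Noncentrality λ = f²N, with 2 and N−3 degrees of freedom. At N=63, λ = 0.16×63 = 10.08 and power is 0.798. At N=66, λ = 0.16×66 = 10.56 and power is 0.818. The smallest equal-group total reaching 80% is 66, so this **reproduces the plan's figure**. With one covariate, power at N=66 is also 0.818.
- *Pearson correlation r=0.4, two-sided, Fisher z.* n = [(1.960+0.842)/atanh(0.4)]² + 3 = (2.802/0.4236)² + 3 ≈ 46.7, so 47 (38 if one-sided). Does not reproduce.
- *Two-group mean difference d=0.4.* 99 per arm two-sided, 78 one-sided. Does not reproduce.

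N=66 therefore fits an F test that is never named and does not fit the one method that is named.

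**3. Would an overall F test be enough?** If one group lies δ SD from two equal groups, f = δ√2/3, so f=0.4 means δ = 0.4×3/√2 = 0.849 SD. Simulation of 200,000 trials with 22 per group:

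| Pattern | Overall F rejects | A–B contrast rejects |
|---|---|---|
| Only C apart by 0.849 SD (A = B) | 0.818 | 0.050 |
| Only B apart by 0.849 SD | 0.817 | 0.791 |

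The F test behaves the same in both rows; only the A–B contrast tells them apart.

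**4. What the A–B contrast will deliver.** Assumptions: normal outcome, equal SDs, no baseline adjustment, two-sided 0.05, SD pooled over three groups. Results are in SD units because the document gives no SD.

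- 22 per group, 63 df: 95% CI half-width = 1.998×√(2/22) = 0.603 SD. Power from the noncentral t with noncentrality d/√(2/22): 0.257 at d=0.4, 0.372 at 0.5, 0.743 at 0.8, 0.791 at 0.849. Power of 80% needs d=0.858.
- A plain two-sample t-test on 42 df is nearly the same: half-width 0.608, and 80% power at d=0.865.
- If the attendance rule removes patients, for example leaving 18 in A and 18 in B (an assumption; the document gives no attrition figure), √(2/18) = 0.333 and the half-width is 0.668 SD with 22 in C (55 df), or 0.669 SD with 18 in every group (51 df). In the latter case power is 0.218 at d=0.4 and 0.653 at d=0.8.

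**The case against.** The best defence is that this is an omission in a very short section, and not a plan to answer the question by correlation. The purpose, the hypothesis, the three-group randomisation and N=66 all point to a group comparison. That is fair as to intent, but intent does not fix a test, a contrast or an interval, and the sample-size paragraph names no test.

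A second defence is technical: a Pearson correlation between an outcome and a 0/1 group code gives the same p-value as a two-sample t-test. That is true in general. The plan, however, correlates the measured variables with one another, and group is assigned, not measured. Even with such coding the result would be a p-value without a difference in outcome units or an interval.

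Third, the power figures in the working describe the sample size, not the cost of the missing test, and specifying the test does not improve them. This stands. They are given so that the A–B result is planned and read with its precision in view. The 18-per-group case is illustrative: the attendance rule can act only on A and B, since C has no exercise sessions, but the effect on the half-width is negligible (0.668 against 0.669 SD).

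Finally, if A versus B is the sole question, a single prespecified A–B contrast would suffice and the overall F test is optional. That is a reasonable alternative layout. It still requires the contrast to be named.

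**Conclusion.** The point holds and must be fixed. The plan specifies no between-group estimate, interval or test, and its one inferential method does not address the stated comparison. This rests on reading the text and needs no numerical assumption.

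That N=66 was derived from a three-group F test is an inference from the arithmetic and needs the sponsor's confirmation. The power and precision figures depend on the normal, equal-variance, unadjusted set-up given above. On that basis, 66 patients give about 82% power for an overall F test at f=0.4, but 80% power for A versus B only if the true difference is about 0.86 SD.

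**What to change.** Rewrite Data Analysis and statistical design so that each primary outcome (SCFA and GLP-1) is compared across the three randomised groups, reporting:

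1. the overall F test;
2. A minus B with its 95% confidence interval, named as the contrast that answers the study question;
3. A minus C and B minus C as secondary contrasts.

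Use ANCOVA where a baseline value is already collected and one-way ANOVA otherwise; the sponsor must confirm which applies to SCFA and GLP-1. State which patients enter the comparison, because the attendance rule restricts A and B but cannot apply to C. Keep the Pearson correlations, labelled exploratory. In the sample-size paragraph, state that N=66 refers to the overall F test, if the sponsor confirms it, and that it does not guarantee 80% power for A versus B.

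Which SCFA analyte is primary, and how multiplicity across the two primary outcomes is handled, are separate questions best settled in the same edit.

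Cost: wording only. No extra patients are needed, and no extra samples, since ANCOVA is used only where baseline values already exist. Precision is unchanged by the edit: the unadjusted A–B half-width stays at about 0.60 SD with 22 analysed per group and is wider with fewer.

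### Plain Pearson correlation at p < 0.05, with no arm term, change score, named pair or multiplicity rule, can report misleading associations

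*Combined protocol and SAP*

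**What the plan says.** The section Data Analysis and statistical design has four bullets: the software, means and standard deviations, the correlation bullet and the significance level. The correlation bullet reads "Pearson correlation coefficient was used to determine the relationship between the measured variables". The next reads "Statistical significance was set at" p < 0.05. Nothing there or elsewhere says which pairs are meant, at which visit, on raw values or changes, within or across arms, or how many tests share the 0.05.

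The variables come from the outcome list and the equipment section. SCFA and GLP-1 ("Glucagon like peptide 1 via Elisa kit") are the primary outcomes. The IBS severity score, IBS-QoL and BMI are secondary. For the SCFA assay the text says "Applying four analytes, including total SCFAs, acetate, propionate, and butyrate, will be targeted", while the heading above it names only butyrate and acetate.

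There are three arms of 22. Two receive different exercise programmes, and all three follow the low FODMAP diet for 12 weeks.

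**The concern.** The Review of Literature says that SCFAs regulate hormones including GLP-1. SCFA and GLP-1 are the two primary outcomes, so their correlation is the natural mechanistic claim to draw from this bullet. A significant r between them could arise only because treatment moved both, with no link between patients treated alike. Other significant results could be arithmetic (a total against its own parts) or chance (many pairs, none singled out beforehand). With no rule fixed in advance, a reader cannot tell a planned finding from a selected one, and the choices of arm, visit and pair can be made after the data are seen.

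**Working it through.** **Inputs.** From the protocol: N = 66 in three arms of 22, effect size 0.4, power 80%, alpha 0.05, and the variables listed above. Assumed: two-sided tests, normal data, and 0.4 read as Cohen's f (the plan does not name the index).

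**The plan's own figure.** For a one-way ANOVA with three groups and f = 0.4, noncentrality is N × f². Power is 0.798 at N = 63 and 0.818 at N = 66. The smallest multiple of three that reaches 80% is therefore 66. The sample size reproduces under this reading, which supports using f = 0.4 below.

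**1. Arms pooled, no arm term.** Take two variables with within-arm SD 1 and no within-arm correlation, each shifted between arms with f = 0.4. The pooled correlation is c × f² / (1 + f²), where c is the correlation between the two arm profiles.
- Same profile, c = 1: r = 0.16 / 1.16 = 0.138. By Fisher's z, 0.139 × √63 = 1.10, so the rejection rate is about P(Z > 1.96 − 1.10) ≈ 20%. Simulation gives 20%. A mirror-image profile gives r = −0.138 and the same rate.
- One variable moved by both exercise arms, the other by HIIT only, c = 0.5: r = 0.08 / 1.16 = 0.069. Simulation gives 8%.
- Orthogonal profiles, c = 0: r = 0, 5%.
- Same profile with f = 0.25: r = 0.0625 / 1.0625 = 0.059, about 7%.

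Change scores alone do not cure this. With within-patient correlation 0.6 (assumed), the within-arm variance of a change is 2 × (1 − 0.6) = 0.8. With the same profile, r = 0.16 / (0.16 + 0.80) = 0.167, and simulation gives 28% false positives.

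**2. Total SCFA against a component.** If the total is the sum of three independent components of equal SD, r = 1/√3 = 0.577. At n = 66 the critical |r| is 0.242, and simulation finds significance in over 99% of runs. If one component has three times the SD of the others, r = 3/√11 = 0.90 for that one and 1/√11 = 0.30 for the others. These are significant in 100% and about 70% of runs.

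**3. Number of pairs.** If all pairs are null and independent, P(at least one hit) = 1 − 0.95^m.

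| SCFA variables counted | Variables | Pairs m | Expected hits (0.05m) | P(at least one) |
|---|---|---|---|---|
| One, as in the outcome list | 5 | 10 | 0.5 | 40% |
| Butyrate and acetate, as in the assay heading | 6 | 15 | 0.75 | 54% |
| Four analytes, as in the assay text | 8 | 28 | 1.4 | 76% |

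Three of the 28 pairs are total against component. The other 25 give 1.25 expected hits and 72% if independent, or 69% by simulation that allows for the shared total.

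**4. Visits pooled (not stated in the plan).** Suppose baseline and week-12 values were stacked as 132 independent rows and both variables shifted by 0.8 SD. The visit means lie ±0.4 from centre, so r is again 0.16 / 1.16 = 0.138, now on 132 rows. Simulation gives 36% to 38% for within-patient correlation 0 to 0.8. With no shift at all, within-patient correlation of 0.5 to 0.8 gives 8% to 13%.

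**Check of the remedy.** Under the same-profile f = 0.4 shift, a partial correlation of changes adjusted for group and both baselines rejected in 4.9% of simulated trials.

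**The case against.** The strongest reply is that the plan is silent rather than wrong. It never says that arms or visits will be pooled, and it gives no measurement schedule from which to build 132 rows. A reader might infer that every pair among eight variables will be tested across all arms and visits, so that artefacts are bound to be reported. The documents do not support that: the word all belongs to the bullet on means and standard deviations, and the SCFA list can be counted in more than one way. This stands, so the conclusion is that the analysis can mislead, and the pair count is a range.

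The 20% also needs matching arm profiles, and the 40% to 76% assumes that every pair is null. Severity and IBS-QoL are probably truly related. Both limits stand.

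A reader might further infer that the correlation is invalid in itself. It is not: a pooled r validly describes marginal association, and if treatment moves both variables that association is real. It is not evidence of a link within arms, and the plan does not say which of the two it seeks.

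The total-against-component pairs are nearly certain to be significant if computed, but they matter least, since few readers would build a mechanism on them. Finally, no hypothesis concerns correlation, and the missing between-group comparison is a larger and separate gap. Adding that comparison would still leave this bullet as it is.

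Analysing each arm separately would remove the arm artefact, but with 28 pairs it means 84 tests, with 84 × 0.05 = 4.2 expected chance hits and a 99% chance of at least one if all are null and independent.

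**Conclusion.** The concern holds in conditional form and should be addressed. An unadjusted correlation across three differently treated arms cannot show that SCFA and GLP-1 are linked among patients treated alike, and nothing in the plan prevents that use.

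The size depends on choices that the plan leaves open. Pooling arms with f = 0.4 in both variables gives 5% to 20% false positives for a within-arm link, the upper figure only when the arm profiles match. The part-whole r of 0.58 rests on independent components of equal SD. Pooling visits, about 37% at a 0.8 SD shift, is a warning about what the wording permits and not a description of the plan. None of this affects N = 66.

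**What to change.** Replace the correlation bullet with wording such as: One association is prespecified, the change in total SCFA with the change in GLP-1 from baseline to week 12, one value per patient, estimated as a partial correlation adjusted for randomised group and both baseline values, with a 95% confidence interval. All other correlations are exploratory and are reported as estimates with confidence intervals, without claims of significance. Total SCFA is not correlated with its components.

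Reconcile the assay heading with the list of four analytes, so that it is clear that total SCFA is measured, and state the two measurement times.

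The cost is wording in the analysis section: no added patients, samples or visits beyond the baseline and week-12 measurements. The downside is that fewer correlations can be called significant. Other adjusted analyses would also serve. The essential features are one named pair, one value per patient and adjustment for arm.
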